11.3.2.4 Supportive/sensitivity analyses

Supportive and sensitivity analyses will be conducted on the PPS and FAS.

Supportive analysis. Change from baseline to Week 8 of DB treatment period (Period II) in mean trough SiDBP (imputed by last observation carried forward, if applicable) will also be analyzed using an analysis of covariance (ANCOVA) model with a factor for

ACT-132577 Essential hypertension Protocol AC-080A201 Version 3 30 May 2016, page 87/112

Confidential

treatment group (placebo and four doses of ACT-132577) and a covariate for baseline mean trough SiDBP. Each of the four doses of ACT-132577 will be compared to placebo applying Dunnett's test). The active comparator will be compared separately versus placebo using an ANCOVA model with a factor for treatment group (placebo or active comparator) and a covariate for baseline mean trough SiDBP.

Sensitivity analysis. Changes from baseline to Weeks 2, 4 and 8 of DB treatment period (Period II) in mean trough SiDBP will also be analyzed using repeated measurements model. A mixed model will be applied with factors for treatment group, time (Week 2, 4 or 8), treatment by time interaction and a covariate for baseline mean trough SiDBP. An unstructured covariance matrix will be used to account for the correlation between repeated measurements from the same subject. At Week 8 each of the four doses of ACT-132577 will be compared to placebo applying Dunnett's test.

11.3.2.5 Subgroup analyses

Subgroup analyses will be performed by age (\leq 65 versus > 65 years), race and country. This will be done based on the ANCOVA and the repeated measurements model described above. Additional subgroup analyses will be described in the SAP.

11.3.3 Analysis of the secondary efficacy variable(s)

Secondary efficacy variables will be analyzed for the PPS at $\alpha = 0.05$ (two-sided) using 95% CIs. No correction for multiple testing will be applied for these analyses.

Change from baseline to Week 8 of DB treatment period (Period II) in mean trough SiSBP will be analyzed similarly to the primary endpoint (SiDBP), i.e., MCP-Mod will be applied, supplemented by the ANCOVA and the repeated measurements model described above.

Control and response rates at Week 8 of DB treatment period (Period II) based on trough SiDBP will be analyzed using a logistic regression model with a factor for treatment group and a covariate for baseline mean trough SiDBP. Control and response rates at Week 8 of Period II based on trough SiSBP will be analyzed similarly.

Change from baseline to Week 8 of DB treatment period (Period II) in 24 h mean DBP based on ABPM will be analyzed using an ANCOVA with a factor for treatment group and a covariate for baseline 24 h mean DBP. Change from baseline to Week 8 of DB treatment period (Period II) in 24 h mean SBP based on ABPM will be analyzed similarly.

Trough to peak ratios for DBP at Week 8 of DB treatment period (Period II) based on ABPM will be log transformed and analyzed using an ANCOVA model with a factor for treatment group and a covariate for log baseline trough to peak ratio.

Essential hypertension Protocol AC-080A201 Version 3 30 May 2016, page 88/112

Confidential

11.3.4 Analysis of the other efficacy variables

Changes from baseline to Week 2 and Week 4 of DB treatment period (Period II) in mean trough SiSBP and SiDBP (OBPM) will be obtained from the same repeated measurements model as described in Section 11.3.2.4 under *sensitivity analysis*.

Change from baseline to Week 8 of DB treatment period (Period II) in mean day time ABPM will be analyzed using an ANCOVA with a factor for treatment group and a covariate for baseline mean day time ABPM. Change from baseline to Week 8 of DB treatment period (Period II) in mean night time ABPM will be analyzed similarly.

Trough to peak ratios for SBP at Week 8 of DB treatment period (Period II) based on ABPM will be analyzed similarly to trough to peak ratio for DBP based on ABPM.

Changes from baseline to Week 2 of withdrawal period (Period III) in mean trough SiSBP and SiDBP (OBPM) will be obtained by extending the repeated measurements model described in Section 11.3.2.4 with a timepoint for Week 2 of withdrawal period (Period III). Changes from Week 8 of Period II to Week 2 of withdrawal period (Period III) in mean trough SiSBP and SiDBP will be obtained from the same model using appropriate treatment and time contrasts.

11.3.5 Analysis of the safety variable(s)

All safety analyses described below will be performed on the Safety Set including data from DB treatment period (Period II). All safety analyses will also be performed on the subset of subjects who participated in the withdrawal period, including data from withdrawal period (Period III). Additionally, summaries will be provided for safety data from Period I based on the Screened Analysis Set. All safety data will be listed, with flags for quantitative abnormalities.

11.3.5.1 Adverse events

A treatment-emergent AE is any AE temporally associated with the use of a study drug. Treatment-emergent is defined as in Section 10.1.1. The number and percentage of subjects experiencing treatment-emergent AEs and SAEs at least once will be tabulated by treatment group and by:

- MedDRA System Organ Class (SOC) and individual Preferred Term (PT) within each SOC, in descending order of incidence.
- Frequency of subjects with events coded with the same PT, in descending order of incidence.

Furthermore, treatment-emergent AEs and SAEs will be tabulated as described above by severity and relationship to study drug.

Essential hypertension Protocol AC-080A201 Version 3 30 May 2016, page 89/112

Confidential

AEs leading to premature discontinuation of study drug and death will also be summarized as described above.

Listings will be provided for all reported AEs, including SAEs. In addition, separate listings will be provided for SAEs, for AEs leading to premature discontinuation of study drug, and for AEs leading to death.

The number and percentage of subjects with treatment-emergent ECG abnormalities will be tabulated by treatment group.

11.3.5.2 Laboratory parameters

Descriptive summary statistics by visit and treatment group will be provided for observed values and absolute changes from baseline, in both hematology and blood chemistry and urine (only UACR) laboratory tests. In order to minimize missing data and to allow for unscheduled visits, all recorded assessments will be assigned to the most appropriate visit timepoint according to the best fitting time-window for that assessment.

Actelion internal guidelines will be used for the definitions of marked abnormalities and for the standardization of numeric values obtained from different laboratories and/or using different normal ranges. Standard numeric laboratory variables are transformed to standard units. All laboratory data transferred are taken into account regardless of whether they correspond to scheduled (per protocol) or unscheduled assessments.

Marked laboratory abnormalities will be summarized for each laboratory parameter by treatment group providing their incidence and frequency. Absolute values and changes from baseline of laboratory parameter values during the course of the study will be summarized using the usual location and scale summary statistics by treatment group.

Laboratory parameters include:

- Hematology: hemoglobin, hematocrit, erythrocyte count, leukocyte count with differential counts, platelet count.
- Blood chemistry: AST, ALT, alkaline phosphatase, total and direct bilirubin, LDH, creatinine, creatinine clearance, uric acid, glucose, sodium, potassium, protein, albumin, free T3, free T4, TSH.
- Urine: UACR.

The number and percentage of subjects with treatment-emergent laboratory abnormalities will be tabulated by treatment group.

Essential hypertension Protocol AC-080A201 Version 3 30 May 2016, page 90/112

Confidential

11.3.5.3 12-lead ECG

Descriptive statistics by visit and treatment group will be provided for observed values and absolute changes from baseline, in numeric 12-lead ECG values (PR, QRS, QT, QTcB and QTcF). In order to minimize missing data and to allow for unscheduled visits, all recorded assessments will be assigned to the most appropriate visit time point according to the best fitting time-window for that assessment.

In addition, treatment-emergent morphological ECG abnormalities will be summarized.

11.3.5.4 Vital signs and body weight

Vital signs parameters, HR and body weight will be summarized at each study visit using the usual location and scale summary statistics by treatment group for both absolute values and changes from baseline. Subjects for whom no post-baseline value is available are excluded from the analysis of the changes from baseline.

11.3.6 Analysis of other variable(s)

PK and PD data will be listed by subject number and PK endpoints will be analyzed descriptively by treatment. PK trough and ET-1 plasma concentrations at each visit will be summarized by treatment using arithmetic mean, minimum, median, maximum, standard deviation (SD), standard error, and two-sided 95% CI of the mean.

If possible, the exploratory PK/PD analysis will be performed in which the relationship between ACT-132577 plasma concentrations and ET-1 levels is investigated.

Whenever possible, a model will be established to describe these relationships. Exploratory data-driven analysis may be performed, with the caveat that any statistical inference will not have any confirmatory value. The results of this analysis will be reported separately.

11.4 Interim analyses

No formal interim analysis is planned.

11.5 Sample size

11.5.1 Sample size justification

In a previous study with macitentan in essential hypertension (AC-055-201) the within-group SD for the change from baseline to Week 8 in SiDBP was 7.4 mmHg (90% CI: 7.0–8.0). In the sample size calculations SDs of 7–9 mmHg are considered.

Essential hypertension Protocol AC-080A201 Version 3 30 May 2016, page 91/112

Confidential

It is assumed that the maximum difference versus placebo is achieved at the highest dose of ACT-132577. For the dose-response curves four scenarios were considered [see Figure 2]. These are, in fact, sigmoidal E_{max} curves.

For the sample size it was required that the power to demonstrate the existence of a dose-response relationship is 90% for each of the four scenarios. A total of 70 subjects per group in the PPS (i.e., 420 subjects in total) satisfied this condition and would also allow for sufficiently precise estimation of the dose-response curve. Assuming a drop-out rate of approximately 20%, a total of 90 patients per group would need to be randomized (i.e., 540 in total).

The power for the MCP-Mod approach to demonstrate the existence of a dose-response relationship with 70 subjects per group (PPS) is given in Table 2 for various combinations of placebo-corrected differences and SDs.

Table 2 Power to demonstrate a dose-response relationship with n = 70 per group (PPS)

	Scenario 1	Scenario 2	Scenario 3	Scenario 4
Delta*	4.9	4.5	4.5	4.0
SD				
7	99%	99%	99%	99%
8	99%	99%	99%	99%
9	98%	96%	98%	97%

^{*}Maximum difference versus placebo (mmHg) PPS = Per-Protocol Set

Conservatively assuming that the difference versus placebo is 4 mmHg and the SD is 9 mmHg, the power for the MCP-Mod approach is > 95% for the four scenarios considered.

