	 Treatment-emergent marked laboratory abnormalities; Changes from baseline to Weeks 2, 4 and 8 of DB treatment period (Period II) in laboratory parameters; Changes from baseline to Weeks 4 and 8 of DB treatment period (Period II) in ECG parameters (PR, QRS, QT, QTcB, QTcF); Changes from baseline to Weeks 2, 4 and 8 of DB treatment period (Period II) in body weight and heart rate. See Section 10.1.1 for definition of 'treatment-emergent'. Pharmacokinetic/pharmacodynamic endpoints Pharmacokinetic / pharmacodynamic endpoints are described in Section 6.2. 					
ASSESSMENTS	in Section 6.3. Refer to the schedule of assessments in Table 1.					
STATISTICAL METHODOLOGY	The Full Analysis Set (FAS) includes all subjects randomized to a study treatment, who have a baseline mean trough SiDBP.					
	The Per-Protocol Set (PPS) includes all subjects from the FAS who have a mean trough SiDBP at Week 8 of DB treatment period (Period II) and do not have any major protocol deviation. Major protocol deviations will be described in the Statistical Analysis Plan.					
	The Safety Set includes all subjects who received at least one dose of study treatment in DB treatment period (Period II).					
	Statistical hypotheses The null hypothesis to be tested is that there is no dose-response for the primary endpoint.					
	H_0 : $\mu_0 = \mu_1 = \mu_2 = \mu_3 = \mu_4$					
	Here, μ_i denotes the mean change from baseline to Week 8 in mean trough SiDBP (μ) for ACT-132577 dose (i) (where $i=0$ corresponds to placebo). A value of $\mu_i < 0$ corresponds to a decrease in SiDBP.					
	The alternative hypothesis is that there is a monotonic dose-response for the primary endpoint.					
	H ₁ : $\mu_0 \ge \mu_1 \ge \mu_2 \ge \mu_3 \ge \mu_4$ and $\mu_i > \mu_j$ for at least one $i > j$ or $\mu_0 \le \mu_1 \le \mu_2 \le \mu_3 \le \mu_4$ and $\mu_i < \mu_j$ for at least one $i > j$					

Note that larger values of μ_i –corresponding to less decrease (or more increase) from baseline to Week 8 in mean trough SiDBP with increasing dose of ACT-132577– are less favorable. The first part of the alternative hypothesis corresponds to ACT-132577 being superior to placebo.

Type I and II errors and power

The type I error (α) is set to 0.05 (two-sided). The type II error is set to 0.10 and therefore the power to 90%.

Primary analysis

The primary analysis will be conducted on the PPS.

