Change from baseline to Week 8 in mean trough office SiDBP will be analyzed using the MCP-Mod approach. In brief, it consists of a set of Multiple Contrast Tests (MCTs) to establish the existence of a dose-response and a set of pre-specified dose-response models to describe the dose-response curve.

Six candidate dose-response models will be considered: linear, linear in log-dose, quadratic, E_{max} , sigmoidal E_{max} and logistic. The analysis will be performed using the R-package DoseFinding. A dose-response relationship is demonstrated if at least one of the six MCTs has an adjusted p-value < 0.05.

Supportive and sensitivity analyses will be conducted on the PPS and FAS. Change from baseline to Week 8 of DB treatment period (Period II) in mean trough SiDBP (imputed by last observation carried forward, if applicable) will also be analyzed using an analysis of covariance model with a factor for treatment group (placebo and four doses of ACT-132577) and a covariate for baseline mean trough SiDBP. Each of the four doses of ACT-132577 will be compared to placebo applying the Dunnett's test.

Secondary analyses

Secondary efficacy variables will be analyzed for the PPS at $\alpha = 0.05$ (two-sided) using 95% confidence intervals (CIs). No correction for multiple testing will be applied for these analyses.

Safety analyses

Safety analyses will be performed on the Safety Set. Safety data will be summarized using descriptive statistics.

Interim analysis

No formal interim analysis is planned.

Sample size

In a previous study with macitentan in essential hypertension (AC-055-201) the within-group standard deviation (SD) for the change from baseline to Week 8 in SiDBP was 7.4 mmHg (90% CI: 7.0–8.0).

It is assumed that the maximum difference versus placebo is achieved at the highest dose of ACT-132577.

For the sample size it was required that the power to demonstrate the existence of a dose-response relationship — conservatively assuming a maximum difference versus placebo of 4 mmHg and an SD = 9 mmHg — is 90%. A total of 70 subjects per group in the PPS (i.e., 420 subjects in total) satisfied this condition and would also allow for sufficiently precise estimation of the dose-response curve. Assuming a drop-out rate of approximately 20%, a total of 90 patients per group would need to be randomized (i.e., 540 in total).

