11.5.2 Sample size sensitivity

The power for the supportive ANCOVA to demonstrate that at least one of the four ACT-132577 doses is better than placebo is given in Table 3 for the same combinations of placebo-corrected differences and SDs.

Table 3 Power for the supportive ANCOVA with n = 70 per group (PPS)

	Scenario 1	Scenario 2	Scenario 3	Scenario 4
Delta*	4.9	4.5	4.5	4.0
SD				
7	99%	98%	97%	97%
8	95%	94%	91%	91%
9	89%	87%	82%	82%

^{*}Maximum difference versus placebo (mmHg) ANCOVA = analysis of covariance; PPS = Per-Protocol Set.

Essential hypertension Protocol AC-080A201 Version 3 30 May 2016, page 92/112

Confidential

Again assuming that the difference versus placebo is 4 mmHg and the SD is 9 mmHg, the power for the pairwise comparisons is > 80% for the four scenarios considered. It can be seen that ANCOVA is less powerful than the MCP-Mod approach.

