11.5.3 Blinded sample size re-estimation

A blinded sample size re-estimation will be performed by the sponsor after 100 subjects have been randomized and their Week 8 BP data are available for analysis (or DB treatment discontinuation before Week 8 is confirmed, where applicable). The sample size recalculation will consider the overall SD of the primary endpoint (change from baseline to Week 8 in mean trough SiDBP, measured by OBPM) in the PPS as well as a more common requirement for the power to detect a dose-response, still allowing for sufficient precision to estimate the dose-response curve [Table 4].

Table 4 Sample size (PPS) needed for 80–95% power to detect a dose-response for various SDs

	SD = 6.0	SD = 6.5	SD = 7.0	SD = 7.5	SD = 8.0	SD = 8.5	SD = 9.0
80% power							
- PPS size	126	150	174	198	222	252	282
- per group*	21	25	29	33	37	42	47
90% power							
- PPS size	174	198	234	264	300	336	378
- per group*	29	33	39	44	50	56	63
95% power							
- PPS size	210	252	288	330	372	420	474
- per group*	35	42	48	55	62	70	79

^{*}Expected number. Power based on the MCT test in the MCP-Mod procedure as implemented in the R *DoseFinding* package, averaged over the four dose-response curves in Figure 2.

Here, SD is the overall standard deviation of the primary endpoint. It is acknowledged that this could be an overestimation of the (unobserved) within group SD, but, given the range of anticipated treatment group differences, this overestimation is likely to be small (< 5%). The recalculated size of the PPS is expected to be between 280 subjects and the originally foreseen 420 subjects.

The number of subjects to be randomized will be calculated by dividing PPS size by the proportion of randomized subjects who were included in the PPS. That proportion will be estimated based on the same 100 randomized subjects considered for the sample size

MCP-Mod = Multiple Comparison procedure - Modeling; MCT = Multiple Contrast Test; PPS = Per-Protocol Set; SD = standard deviation.

Essential hypertension Protocol AC-080A201 Version 3 30 May 2016, page 93/112

Confidential

re-estimation. To be conservative, the lower limit of the 95% CI around the proportion will be employed, of which some examples are given in Table 5.

Table 5 Number and proportion of subjects in PPS and 95% CIs for the proportion at the time of the sample size re-estimation

Number	Number	Proportion	95% CI*	
Randomized	in PPS	in PPS		
100	95	0.95	0.89	0.98
100	90	0.90	0.82	0.95

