9 GENERAL STATISTICAL METHODOLOGY

A blinded SSR will be performed by the sponsor after 100 subjects have been randomized and their Week 8 (time window Visit 7) OBPM data are available for analysis. The SSR will consider the overall standard deviation (i.e., based on pooled treatment groups as the SSR is blinded) of the primary endpoint (change from baseline to Week 8 [time window Visit 7] in mean trough SiDBP, measured by OBPM) in the PPS.

The primary endpoint (change from baseline to Week 8 [time window Visit 7] of double-blind treatment period in mean trough SiDBP) will be analyzed using the MCP-Mod approach [Bretz 2005, Pinheiro 2006, EMA 2013]. The blinded SSR will be based on the average power achieved in the MCP-Mod approach, to detect a dose response when the ‘true’ dose-response curve is among the four curves displayed in Figure 1 (copied from protocol figure 2). All four assume that the minimum response will be obtained with placebo (0 mg) and the maximum response (4–5 mmHg, placebo corrected) will be reached at the highest dose of ACT-132577 (50 mg).

Figure 1 Dose response relationships used in power calculations

[figure not shown]

For each of the four dose-response curves the power will be calculated using the `powMCT` function in the R-package `DoseFinding` [Bornkamp 2016]. R-code is included in Appendix 15.1.

The calculation requires an estimate of the standard deviation of the primary endpoint [see Section 10.6] in the PPS. The *average* power is displayed in Figure 2 for primary endpoint SDs ranging from 6–9 mmHg. (For the original sample size calculation 9 mmHg was assumed and > 95% power was required for each of the four scenarios separately.)

Figure 2 Average power to detect dose response

Black SD = 6.0; Red SD = 6.5; Blue SD = 7.0; Green SD = 7.5; Orange SD = 8.0; Purple SD = 8.5; Grey SD = 9.0.

The associated sample sizes (PPS) for 80–95% average power are given in [Table 2](#).

Table 2 Sample size (PPS) needed for 80–95% power to detect a dose-response across various SDs

	SD = 6.0	SD = 6.5	SD = 7.0	SD = 7.5	SD = 8.0	SD = 8.5	SD = 9.0
80% power							
- PPS size	126	150	174	198	222	252	282
- per group*	21	25	29	33	37	42	47
85% power							
- PPS size	144	168	198	222	258	288	318
- per group*	24	28	33	37	43	48	53
90% power							
- PPS size	174	198	234	264	300	336	378
- per group*	29	33	39	44	50	56	63
95% power							
- PPS size	210	252	288	330	372	420	474
- per group*	35	42	48	55	62	70	79

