# power
sigs <- seq (6,9,0.5)
nn <- seq (20,70,1)

pow<-matrix(NA,length(sigs)*length(nn),6)
k <- 1
for (i in 1:length(sigs)){
  for (j in 1:length(nn)){
    pow[k,1] <- sigs[i]
    pow[k,2] <- nn[j]
    pow[k,3] <- round(powerMCT (d4, sigs[i]/5, nn[j], black), 3)
    pow[k,4] <- round(powerMCT (d4, sigs[i]/4.5, nn[j], red), 3)
    pow[k,5] <- round(powerMCT (d4, sigs[i]/4.5, nn[j], blue), 3)
    pow[k,6] <- round(powerMCT (d4, sigs[i]/4, nn[j], green), 3)
    k <- k+1
  } # j
} # i

plot(pow[pow[,1]==6,2], rowMeans(pow[pow[,1]==6,3:6]), type="l", col="grey",
      xlab="group size (PPS)", ylab="power", xlim=c(20,70), ylim=c(0.6,1))
cols <- c("black","red","blue","green","orange","purple","grey")

for (i in 1:7){
  sel <- pow[pow[,1]==sigs[i],]
  lines(sel[,2], rowMeans(sel[,3:6]), col=cols[i])
}
abline (h=c(0.8, 0.9, 0.95), col="grey")
```

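### The power figures in protocol Tables 2 and 3 correspond to a 5 mmHg difference in every scenario, not to the stated 4.9/4.5/4.5/4.0 mmHg; at 4 mmHg and SD 9 the power is about 85–90% (MCP-Mod) and 60–70% (Dunnett)

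*Protocol*

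**What the plan says.** Protocol Section 11.5.1 sets the design condition: "it was required that the power to demonstrate the existence of a dose-response relationship is 90% for each of the four scenarios". It states that 70 subjects per group in the Per-Protocol Set meet it. Table 2 gives the MCP-Mod power at that size for maximum placebo-corrected differences of 4.9, 4.5, 4.5 and 4.0 mmHg in scenarios 1 to 4. At SD 9 the row reads 98/96/98/97%. The text then takes 4 mmHg and SD 9 as a conservative case and says that "the power for the MCP-Mod approach is > 95% for the four scenarios considered".

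Section 11.5.2 and Table 3 do the same for the supportive ANCOVA with Dunnett's test. The SD 9 row reads 89/87/82/82%, and for 4 mmHg and SD 9 the text says that "the power for the pairwise comparisons is > 80% for the four scenarios considered".

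The protocol synopsis, repeated in Appendix A of the main SAP, ties the 90% requirement to one case, "conservatively assuming a maximum difference versus placebo of 4 mmHg and an SD = 9 mmHg". Section 9 of the re-estimation SAP gives a different requirement: "For the original sample size calculation 9 mmHg was assumed and > 95% power was required for each of the four scenarios separately".

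Table 4 in protocol Section 11.5.3 lists the sizes needed for given power, "averaged over the four dose-response curves in Figure 2". At SD 9 it asks for 47, 63 and 79 per group for 80%, 90% and 95%.

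**The concern.** Two conflicts can be seen without any calculation.

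- **Table 2 against Table 4.** Both rest on the same four curves. Power rises with sample size, so by Table 4 the average power at 70 per group and SD 9 lies between 90% (n = 63) and 95% (n = 79). The Table 2 row averages (98 + 96 + 98 + 97)/4 = 97.25%.
- **Within Table 3.** Scenarios 3 and 4 have the same power at every SD (97/97, 91/91, 82/82), although their stated differences are 4.5 and 4.0 mmHg.

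At stake is the case for 70 per group. The 4 mmHg, SD 9 combination is presented as the conservative planning point, and Section 10.6.3 of the main SAP calls 4 mmHg the clinically relevant reduction. If the printed power belongs to a larger effect, the chance of missing a real dose-response at that point has been understated.

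**Working it through.** **Inputs**

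- Alpha 0.05 two-sided (protocol synopsis). n = 70 per group, five groups (placebo and four doses), so df = 5 × 70 − 5 = 345.
- Doses 0, 5, 10, 25, 50 mg and the six candidate models with their starting values (re-estimation SAP, Appendix 15.2; its doses are in units of 100 mg).
- True curves, same appendix: sigmoidal Emax with ED50/ED90 of 12.5/25, 12.5/50, 25/50 and 25/75 mg. Hill coefficient h = ln 9/(ln ED90 − ln ED50) = 3.17, 1.58, 3.17, 2.00.
- Scenarios 1 to 4 are taken to be these curves in that order.

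**Formulae**

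- Mean difference from placebo at dose d: Δ·f(d)/f(50), with f(d) = d^h/(ED50^h + d^h).
- MCP-Mod: reject if the largest of the six |√n·c′ȳ/s| exceeds the critical value, where c is the unit-length optimal contrast of a candidate model. Critical value about 2.17.
- Dunnett: reject if the largest of the four |ȳ_i − ȳ_0|/(s·√(2/n)) exceeds about 2.45.
- Power by simulation, at least 1 million draws per cell; results are stable to about 0.1 point.

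**Check of the method against Table 4.** The appendix code divides the SD by 5, 4.5, 4.5 and 4 for the four curves; the last call begins "powerMCT (d4, sigs[i]/4, nn[j], green". With those differences, average power at SD 9 is about 80.7% at n = 47, 90.2% at 63 and 95.2% at 79. At SD 8.5, n = 70 gives 95.1%; at SD 8, n = 50 gives 90.3%. These agree with Table 4. At n = 70 and SD 9 the average is 92.8%.

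**Tables 2 and 3 at n = 70 (scenarios 1/2/3/4, %)**

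| Test | SD | Printed | Stated differences 4.9/4.5/4.5/4.0 | 5 mmHg in all |
|---|---|---|---|---|
| MCP-Mod | 7 | 99/99/99/99 | 99.9/99.1/99.5/97.7 | 100.0/99.8/99.9/99.9 |
| MCP-Mod | 8 | 99/99/99/99 | 99.5/96.7/97.8/93.4 | 99.6/98.8/99.3/99.1 |
| MCP-Mod | 9 | 98/96/98/97 | 98.0/92.0/94.1/86.7 | 98.3/96.3/97.5/97.1 |
| Dunnett | 7 | 99/98/97/97 | 98.3/94.9/92.3/84.7 | 98.7/98.1/96.8/96.9 |
| Dunnett | 8 | 95/94/91/91 | 94.3/87.4/83.0/72.8 | 95.1/93.6/90.7/91.0 |
| Dunnett | 9 | 89/87/82/82 | 87.4/78.0/72.2/61.3 | 88.8/86.6/81.9/82.4 |

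With 5 mmHg throughout, all 12 Table 3 cells round to the printed values and all 12 Table 2 cells lie within 1 point. With the stated differences, 7 of 12 cells in Table 2 and 3 of 12 in Table 3 lie within 2 points. The worst gaps are about 10 and 21 points, both in scenario 4 at SD 9.

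**Hand check, top dose against placebo, Dunnett, SD 9 (normal approximation).** The standard error is 9 × √(2/70) = 1.521. For 4 mmHg: 4/1.521 = 2.63, and Φ(2.63 − 2.45) is about 57%. For 5 mmHg: 5/1.521 = 3.29, and Φ(3.29 − 2.45) is about 80%. The lower doses add a few points, giving 61% and 82% in scenario 4. Table 3 prints 82% under a difference of 4.0.

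**The conservative case: 4 mmHg in all four shapes, SD 9, n = 70**

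- MCP-Mod 90.4/84.9/87.8/86.7%, average 87.4% (stated >95%).
- Dunnett 70.0/67.1/60.5/61.3% (stated >80%).

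**Where the 90% requirement holds.** At the stated differences MCP-Mod power is 99.8/98.4/99.1/96.3% at SD 7.4 and 98.9/94.6/96.2/90.3% at SD 8.5. At SD 9, scenario 4 needs about 78 per group for 90%; all four shapes at 4 mmHg need about 83.

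**Likely cause (inferred).** A 5 mmHg asymptote gives 5 × f(50) = 4.94, 4.50, 4.50 and 4.00 mmHg at 50 mg, which are the printed differences. The power then appears to have been computed with each curve reaching the full 5 mmHg at 50 mg.

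**The case against.** The best defence has five parts.

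1. **Some cells fit either way.** This is true of scenario 1, where 4.9 is close to 5, and of the low SDs in Table 2. A 5 mmHg effect at SD 7 also gives 99.8–100%, so matching the printed 99% assumes the table was capped. The evidence is therefore the two tables as a whole, above all Table 3 and the SD 9 row of Table 2.
2. **The planned test adjusts for baseline, which lowers the residual SD.** A 5% reduction would bring scenario 4 to about 90% at a nominal SD of 9. That needs a baseline–change correlation of about 0.31, since √(1 − 0.31²) = 0.95, and the documents give none. Table 4 makes no such allowance. No reduction between 5% and 20% reproduces both tables: 15% fits all of Table 2 but only 4 of 12 cells in Table 3. One-sided testing and n = 84 or 90 also fail.
3. **The 4 mmHg sentences are ambiguous.** They may mean scenario 4 alone. They fail on that reading too, at 86.7% against >95% and 61% against >80%.
4. **Nothing operative depends on these tables.** This stands. The re-estimation used 5/4.5/4.5/4, the main SAP records 490 as the resulting number to randomize, and Table 3 concerns a supportive analysis.
5. **The cause is not proven.** This also stands. The code behind Tables 2 and 3 is not in the documents and Figure 2 is not shown.

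**Conclusion.** The concern holds. Tables 2 and 3 overstate power for the differences printed above them, and the sentences claiming >95% and >80% at 4 mmHg and SD 9 are wrong on either reading. In scenario 4 at SD 9 the chance of missing a true dose-response is about 13%, not 3%; for the Dunnett comparison it is about 39%, not 18%.

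The practical reach is limited. At the stated differences, 70 per group gives at least 90% MCP-Mod power in every scenario up to about SD 8.5, which covers the previous study's SD of 7.4 (90% CI 7.0–8.0). At SD 9 the requirement fails in scenario 4 only. The synopsis condition of 90% at 4 mmHg and SD 9 is reached for one curve shape of four. The >95% per scenario cited in the re-estimation SAP is reached at SD 9 only in scenario 1.

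The result assumes that the scenarios are the appendix curves in code order, which the 4.94/4.50/4.50/4.00 values support, and that the SD is not reduced for baseline adjustment.

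**What to change.** 1. Restate **Table 2** for n = 70 and the stated differences: SD 7 >99/99/>99/98%; SD 8 >99/97/98/93%; SD 9 98/92/94/87%.
2. Restate **Table 3** (two-sided Dunnett): SD 7 98/95/92/85%; SD 8 94/87/83/73%; SD 9 87/78/72/61%. The sponsor should confirm both tables with its own code.
3. In the 4 mmHg, SD 9 sentences of Sections 11.5.1 and 11.5.2, give about 85–90% for MCP-Mod and about 60–70% for the pairwise comparisons, and say that 4 mmHg is applied to all four shapes.
4. State in Section 11.5.1 that 70 per group gives at least 90% in each scenario up to about SD 8.5, and about 87% in scenario 4 at SD 9. Correct the synopsis and its copy in Appendix A of the main SAP to match.
5. Reconcile the 90% requirement in protocol Section 11.5.1 with the >95% in Section 9 of the re-estimation SAP.

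The cost is wording only, with less favourable stated power. No patients are added and the re-estimated sample size does not change.
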